11.1. Primary Objective(s)

Primary Objective #1

Evaluate the impact of the intervention on the diagnosis of SND.

Hypothesis

The primary objective will be tested with the following hypothesis:

$$H_0: p_{1t} = p_{2t}$$

$$H_A: p_{1t} \neq p_{2t}$$

where p_{1t} is the proportion of patients with SND in Phase I and p_{2t} is the proportion of patients with SND in Phase II at time point t .

Endpoint Definition

The absolute change in the proportion of subjects diagnosed with SND at pre-specified time points ($\% = \text{number diagnosed} / \text{number enrolled} \times 100$ at time point $t = 6$, or t is a multiple of 6 representing any additional 6-month interval for which there is sufficient follow-up information) and the absolute change in the number of subjects diagnosed with SND per person-year.

Analysis Methods

A. Statistical Methodology

To compare the proportion of subjects with an SND diagnosis pre-intervention (Phase I) to the proportion post-intervention (Phase II), a binomial exact test will determine statistical significance. The proportion of subjects diagnosed will be evaluated at multiple time points because the time to diagnosis is expected to vary by hospital. Thus, times are pre-specified starting at 6 months and any additional 6-month interval thereafter for which there is sufficient follow-up data available to compare study phases. Proportions calculated at all available time points will be reported. Additionally a Poisson regression will compare the average number of subjects with an SND diagnosis in Phase I and Phase II where the subject time in study is treated as an offset in the model. The above described tests will be performed separately within site as well as overall.

B. Determination of Patients/Data for Analysis

All subjects that are enrolled in the study and that meet study inclusion/exclusion criteria will be included in the determination of the proportion estimates. The proportion estimates will be calculated based on information from fixed time points at 6 months of follow-up, and any additional 6-month interval thereafter for which there is sufficient follow-up data available to compare study phases. The number of subjects that obtain a SND diagnosis by pre-specified time point t is included in the numerator and the number of subjects enrolled is included in the denominator.

Sample Size Methods and Assumptions

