The proportion of SND diagnoses in subjects with bradycardia is currently unknown. The power calculations conservatively assume that the SND diagnosis will be 10% at six months of follow-up, or equivalently an SND incidence of 0.2 diagnoses per person-year. If 200 subjects are collected each in Phase I and in Phase II, assuming a type I error of 0.05 and power of 0.80, a binomial exact test will detect an increase in SND diagnosis of at least 10%. For example, the study will find a statistically significant difference between a Phase I SND percentage of 10% at 6 months and a Phase II SND percentage of 20% at 6 months. If the proportion of SND diagnoses is smaller than 10%, there will be more power to detect significant differences in the diagnosis proportion. It is expected that the study attrition rate may be 5% of the study population. To account for attrition, the sample size for Phase I will be a minimum of 210 subjects and for Phase II will be a minimum of 210 subjects.

Primary Objective #2

Evaluate the impact of the intervention on SND subjects receiving a referral for an indicated IPG device.

Hypothesis

The primary objective will be tested with the following hypothesis:

$$H_0: p_{1t} = p_{2t}$$

$$H_A: p_{1t} \neq p_{2t}$$

where p_{1t} is the proportion of patients referred for an IPG in Phase I and p_{2t} is the proportion of patients in Phase II at time point t .

Endpoint Definition

The absolute change in the proportion of subjects receiving therapy referral for an indicated IPG at pre-specified time points ($\% = \text{number receiving IPG}/\text{number with SND diagnosis} \times 100$ at time point t where $t = 3, 6$, and any additional 3-month interval for which there is sufficient follow-up information) and the absolute change in the number of subjects implanted per person-year.

Analysis Methods

Statistical Methodology

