To compare the proportion of SND subjects that receive a referral for indicated therapy pre-intervention (Phase I) to the proportion post-intervention (Phase II), a binomial exact test will determine statistical significance. The proportion of subjects diagnosed will be evaluated at multiple time points because the time from diagnosis to implant is expected to vary by hospital. Shorter time intervals will be used to evaluate the proportion of referrals than for the proportion of diagnosis because implants typically occur more quickly than the SND diagnosis. Thus, times are pre specified starting at 3 months and any additional 3-month interval thereafter for which there is sufficient follow-up data available to compare study phases. Proportions calculated at all available time points will be reported. Additionally, a Poisson regression will compare the average number of subjects with an implant where the subject time in study beginning at the time of SND diagnosis is treated as an offset in the model.

Determination of Patients/Data for Analysis

The number of subjects that meet inclusion criteria and obtain an SND diagnosis shall be included in this analysis. The proportion estimates will be calculated based on information from fixed time points at 3 months of follow-up, 6 months of follow-up, and any additional 3-month interval thereafter for which there is sufficient follow-up data available to compare study phases. The number of subjects that obtain an IPG referral by pre-specified time point $t = 3, 6, \text{ etc.}$, will be included in the numerator and the number of subjects with an SND diagnosis will be included in the denominator.

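### Two primary objectives are tested at several times with no decisive time point or success rule, and the 10% Phase I rate is called conservative without evidence that it is a ceiling

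*Combined protocol and SAP*

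**What the plan says.** Section 11 names two primary endpoints: diagnosis of SND, and referral of SND subjects for an IPG. For each, section 11.1 says that "a binomial exact test will determine statistical significance", with a Poisson regression as an addition.

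- **Objective 1** has two measures: "The absolute change in the proportion of subjects diagnosed with SND at pre-specified time points" and "the absolute change in the number of subjects diagnosed with SND per person-year". The time points are 6 months and any later multiple of 6 with enough follow-up. On sites, "The above described tests will be performed separately within site as well as overall".
- **Objective 2** follows a shorter grid: "Thus, times are pre specified starting at 3 months and any additional 3-month interval thereafter for which there is sufficient follow-up data available". It has no sample-size paragraph.

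The sample-size text for Objective 1 calls the SND proportion unknown and continues: "The power calculations conservatively assume that the SND diagnosis will be 10% at six months of follow-up". With 200 subjects per phase, "assuming a type I error of 0.05 and power of 0.80, a binomial exact test will detect an increase in SND diagnosis". The size of that increase is put at 10% or more and illustrated as 10% against 20% at 6 months. It adds: "If the proportion of SND diagnoses is smaller than 10%, there will be more power to detect significant differences in the diagnosis proportion". The 200 becomes a minimum of 210 to allow for 5% attrition. Section 11 says the proportions have been estimated, but gives neither the estimate nor a range.

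**The concern.** **Decision rule (main point).** Two primary objectives, each tested at an open-ended series of times, give several routes to a significant primary result. How much follow-up is enough for a later look is undefined, so the number of looks could be settled after data are in hand. The plan does not say which look decides, or whether one objective or both must succeed. A reader of the final report could not tell what the 0.05 in the sizing text protects.

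**Base rate (second point).** A planning value is conservative if the truth is likely to be kinder to the study. For a fixed absolute gain, a base rate above 10% is harsher. The plan discusses only rates below 10%. If the true Phase I rate were higher, a null result could be misread as no effect of the intervention when the study simply had less power than stated.

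**Working it through.** **1. Which looks are possible.** Section 4.3 expects about 6 months of enrollment per phase. Sections 4.3 and 5.4 end data collection 6 months after the last enrollment. The last subject enrolled therefore has 6 months of follow-up and the first about 12. All subjects can reach Objective 1 at 6 months and Objective 2 at 3 and 6 months. With uniform enrollment about half can reach 9 months, and essentially only the first can reach 12. Section 4 says subjects should be followed for approximately 6 months.

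**2. Type I error if either objective could carry the claim.** This rule is an assumption. As a rough anchor, two independent tests at 0.05 give 1 - 0.95² = 0.0975. The actual tests are discrete and the looks are correlated, so I simulated at least 8,000 trials per setting.

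Assumptions: 210 per phase; identical phases; uniform enrollment over 6 months; collection to 6 months after the last enrollment; exponential time to diagnosis with 10% at 6 months; exponential time from diagnosis to referral with 30, 50 or 80% within 3 months; times counted from enrollment. As in section 11.1, the denominator is all enrolled subjects for Objective 1 and diagnosed subjects for Objective 2. Each test is two-sided at 0.05. Within-site and Poisson tests are not counted.

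| Tests able to carry a claim | Fisher | Unconditional exact |
|---|---|---|
| Both objectives, 6 months only | 0.06-0.07 | 0.09-0.10 |
| Objective 1 at 6; Objective 2 at 3 and 6 | 0.07-0.09 | 0.11-0.13 |
| Objective 1 at 6 and 12; Objective 2 at 3, 6, 9 and 12 | 0.14-0.16 | 0.19-0.22 |

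Objective 1 alone, significant at 6 or 12 months, gives 0.05-0.06 (Fisher) or 0.08 (unconditional).

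**3. The plan's own power figure.** Inputs from section 11.1: 10% against 20%, 200 per phase, alpha 0.05, two-sided from the stated alternative. Normal approximation with pooled null variance:

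- null SE = √(2 × 0.15 × 0.85 / 200) = 0.0357
- alternative SE = √((0.09 + 0.16) / 200) = 0.0354
- power = Φ((0.10 - 1.96 × 0.0357) / 0.0354) = Φ(0.849) = 0.802

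Full enumeration over both binomials gives 0.798 for an unconditional exact test (pooled-Z ordering, maximum size at most 0.05) and 0.768 for two-sided Fisher. Fisher reaches only 0.792 with all 210. The stated 0.80 therefore holds for one standard exact test and not for the other.

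**4. The effect of the base rate.** For a gain of 0.10 the variance term is p₁(1 - p₁) + p₂(1 - p₂): 0.25 at a 10% base, 0.315 at 15%, 0.37 at 20%, 0.45 at 30%, and a maximum of 0.495 at 45%. Power moves the other way. Bases above 10% are illustrative assumptions. Cells show Fisher / unconditional exact:

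| Phase I to Phase II | 200 per phase | 210 per phase |
|---|---|---|
| 10% to 20% | 0.768 / 0.798 | 0.79 / 0.83 |
| 15% to 25% | 0.665 / 0.695 | 0.69 / 0.73 |
| 20% to 30% | 0.597 / 0.624 | 0.62 / 0.66 |
| 30% to 40% | 0.518 / 0.540 | 0.54 / 0.57 |

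At 210 per phase power drops below 0.80 once the base exceeds 9.7% (Fisher) or 11.2% (unconditional).

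**5. Absolute or relative gain.** The endpoint is worded as an absolute change, and the plan's remark that lower rates give more power is true only on that scale. For a doubling from 5% to 10%, power at 200 per phase would be 0.41-0.46.

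**The case against.** **The time point for Objective 1 is implied.** The sizing is at 6 months, and 6 months is the first time listed. That is fair, and Objective 1 alone shows little inflation with Fisher. But no analysis text makes 6 months decisive, and Objective 2 has neither a named time nor a stated power.

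**Later looks may never happen.** They require enough follow-up, section 4 plans about 6 months per subject, and section 5.6 allows earlier exits. This stands: the bottom row of the type I error table is a worst case. Later looks are still not excluded, because the threshold is undefined and enrollment continues until 210 is reached.

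**Stronger readings that the documents do not support.** A reader might infer that the trial runs a false-positive risk of up to 0.22. That needs an either-objective, any-time rule that the plan never states. If both objectives had to succeed at one named time each, there would be no inflation. A reader might also treat the Poisson models as rival primary tests, but the plan gives the decision to the exact test.

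**The sample size is not miscalculated.** This also stands. A reader might infer that the study is underpowered, but 0.80 reproduces at the plan's inputs, the sentence on rates below 10% is correct, and no document gives a Phase I rate of 15-30%. Section 11 mentions an estimate, and 10% may be it. In addition, 210 is a minimum: 250 per phase, an even split of the cap of 500, gives 0.77-0.80 at a 15% base.

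**Conclusion.** The point holds as two gaps in the text, and the first is the more important. The plan lets exact tests decide significance for two primary objectives over an open set of times, without a decisive time or a rule across objectives. Under an either-objective rule, type I error would be about 0.06-0.07 (Fisher) or 0.09-0.10 (unconditional) at 6 months only. It would be 0.07-0.09 or 0.11-0.13 at the times all subjects can reach, and 0.14-0.16 or 0.19-0.22 only if 9- and 12-month looks also counted. These figures rest on that assumed rule and on the simulation settings listed above.

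Second, *conservatively* is unsupported. The chance of missing a true 10-point gain with 210 per phase would be 34-38% at an illustrative 20% base, not 20%. Whether 10% is in fact a ceiling cannot be judged from the documents. The unnamed exact test is a minor matter, worth about 3 points of power, but it must be settled before power can be restated.

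The changes should be made. Neither gap makes the design unsound.

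**What to change.** **Analysis text, section 11.1.**
- Make the overall 6-month exact test confirmatory for Objective 1.
- Name one time point for Objective 2, and say whether it runs from enrollment or from diagnosis.
- Test in fixed sequence, Objective 1 then Objective 2, each at two-sided 0.05.
- Label other times, per-person-year (Poisson) analyses and within-site tests as supportive.

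**Sample-size text, section 11.1.**
- Delete *conservatively*, or give the basis for 10% as an upper bound.
- Write the gain as 10 percentage points.
- Name the two-sided exact test and restate power for it.
- Show power for base rates of 10-30% at 210 per phase.

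**Cost.** No added patients. Objective 2 can be claimed only if Objective 1 succeeds, fewer tests can support a primary claim, and the displayed power is less favourable. The sequence keeps Objective 1 at 0.05, so its power is unchanged. Splitting alpha to 0.025 would cut that power to 0.700 (Fisher) or 0.742 (unconditional) at 210 per phase for 10% against 20%. Requiring both objectives also keeps 0.05, but ties success to Objective 2, which has no stated power and would have only about 21 against 42 diagnosed subjects (10% and 20% of 210).

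### Primary Objective #2 is about referral, but its endpoint formula, person-year rate and Poisson model count implants, repeating Secondary Objective #1

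*Combined protocol and SAP*

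**What the plan says.** Sections 4.1 and 11 both present the second primary objective as referral of SND subjects for an indicated IPG. In section 11.1 the Phase I parameter of the hypothesis "is the proportion of patients referred for an IPG in Phase I", and the endpoint definition opens with "The absolute change in the proportion of subjects receiving therapy referral for an indicated IPG at pre-specified time points". The exact test compares proportions referred. The paragraph on patients and data for analysis puts subjects with an IPG referral by time t in the numerator and subjects with an SND diagnosis in the denominator.

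Three elements of the same objective count a different event:

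- The bracketed formula in the endpoint definition has "number receiving IPG" as its numerator.
- The second half of the endpoint definition is "and the absolute change in the number of subjects implanted per person-year".
- In the methodology, "a Poisson regression will compare the average number of subjects with an implant", with time in study from SND diagnosis as the offset.

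The reasons given for the time points are also about implants: "because the time from diagnosis to implant is expected to vary by hospital" and "because implants typically occur more quickly than the SND diagnosis".

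**The concern.** The rate is part of a primary endpoint definition and the Poisson model is one of the analyses listed for that endpoint. If both count implants, neither can show whether the intervention changed referral.

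The plan treats referral and implant as separate steps. Section 1.1 attributes under-treatment to too few referrals to implanters, and implant has its own objective in section 11.2. Section 5.6 provides for the exit of subjects who meet an SND indication but will not be paced, and Ancillary Objective #1 describes those who decline. The plan therefore expects some indicated subjects to go without an implant.

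For the proportion, the endpoint formula and the later numerator statement disagree, and nothing says which prevails. An analyst who follows the formula reports the secondary result as the primary one. The choice could also be made after the data are seen.

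**Working it through.** **1. The three objectives side by side (sections 11.1 and 11.2)**

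| Element | Primary #1 | Primary #2 | Secondary #1 |
|---|---|---|---|
| Objective and hypothesis | diagnosis | referral | implant |
| Endpoint in words | diagnosis | referral | indicated therapy (implant) |
| Formula numerator | diagnosed | received IPG | received IPG |
| Person-year rate | diagnosis | **implant** | implant |
| Exact test | diagnosis | referral | indicated therapy (implant) |
| Numerator in analysis-set text | diagnosis | referral | implant |
| Poisson outcome | diagnosis | **implant** | implant |

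Only Primary Objective #2 mixes two events. Its rate wording and Poisson sentence are word for word those of Secondary Objective #1. The analysis set (subjects who meet the inclusion criteria and obtain an SND diagnosis) and the offset are also the same. Same outcome, same subjects and same offset give the same overall estimate, so this duplication follows from the text alone.

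**2. The plan's own figure**

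No sample size, power or assumed rate is given for Primary Objective #2. The only calculation is for Primary Objective #1: 200 per phase, 10% against 20%, alpha 0.05, power 0.80. The pooled normal formula reproduces it:

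n = [1.960·√(2·0.15·0.85) + 0.842·√(0.10·0.90 + 0.20·0.80)]² / 0.10² = 199 per phase, with power 80.2% at 200.

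This does not bear on the point, except that it supplies plausible denominators for Objective #2: 200 × 0.10 = 20 and 200 × 0.20 = 40 diagnosed subjects.

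**3. Illustration for the proportion**

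Assumptions, none from the documents: referral probabilities r1 and r2, and a share c of referred subjects who are implanted. Referred subjects are binomial(n, r), and implanted subjects given referred are binomial(referred, c), so the implant probability is r·c. The test is a two-sided Fisher exact test, significant if p ≤ 0.05. All probabilities come from full enumeration, not simulation.

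Single tables with 20 and 40 diagnosed:

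| Numerator | Phase I | Phase II | p |
|---|---|---|---|
| Referral | 10/20 | 32/40 | 0.034 |
| Implant, c = 0.9 | 9/20 | 29/40 | 0.049 |
| Implant, c = 0.8 | 8/20 | 26/40 | 0.097 |
| Implant, c = 0.6 | 6/20 | 19/40 | 0.269 |

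Power at referral 50% against 80% is 0.616 for referral. For implants it is 0.487 (c = 0.9), 0.345 (c = 0.8), 0.204 (c = 0.6) and 0.161 (c = 0.5).

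Probability that the two numerators disagree on significance, for selected referral pairs:

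| Referral | c = 0.9 | c = 0.8 | c = 0.6 | c = 0.5 |
|---|---|---|---|---|
| 30% vs 50% | 0.101 | 0.143 | 0.196 | 0.214 |
| 50% vs 60% | 0.054 | 0.072 | 0.091 | 0.096 |
| 50% vs 80% | 0.198 | 0.324 | 0.453 | 0.495 |
| 50% vs 90% | 0.151 | 0.300 | 0.573 | 0.649 |
| 50% vs 95% | 0.105 | 0.232 | 0.562 | 0.657 |
| 70% vs 90% | 0.237 | 0.305 | 0.387 | 0.403 |

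Over eleven referral pairs, disagreement runs from 5% to 57% for c between 0.9 and 0.6, and reaches 66% at c = 0.5. At c = 1 the two always agree.

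The gap can also run the other way. Suppose referral is flat at 80% in both phases and c rises to 0.9 in Phase II:

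| c in Phase I | Implant probability, Phase I vs II | Implant test significant | Referral test significant |
|---|---|---|---|
| 0.7 | 0.56 vs 0.72 | 0.208 | 0.035 |
| 0.6 | 0.48 vs 0.72 | 0.405 | 0.035 |
| 0.5 | 0.40 vs 0.72 | 0.624 | 0.035 |

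**The case against.** The strongest reply is that the main inference is already correctly specified. The hypothesis, the exact test that decides significance, and the stated numerator and denominator all use referral. The Poisson model is introduced only as an addition, and no hypothesis is stated for a rate. One bracketed phrase is outweighed by every other statement of the objective and looks like text carried over from the secondary objective. The power figures concern the proportion, where the text already leans towards referral, and they rest on assumed rates and on the Primary Objective #1 alternative being true.

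Much of this stands for the proportion: a careful analyst would probably use referral, and the figures are illustrative. It does not rescue the rate or the Poisson model. The rate sits inside the primary endpoint definition, and neither has a referral version elsewhere to fall back on. Loose wording is not a sufficient explanation either. The words used for the rate and the Poisson outcome cannot mean referred, and section 11.2 uses the same words where implant is plainly intended.

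**Conclusion.** The point holds and should be corrected before analysis. From the text alone, half of the endpoint definition for Primary Objective #2 and its Poisson model measure implants. The plan contains no person-year or Poisson analysis of referral, and the overall Poisson result duplicates Secondary Objective #1.

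The conflict over the proportion is the lesser part, because the exact test and its numerator already name referral. Its size depends on assumed referral rates, the share of referred subjects implanted, and 20 and 40 diagnosed subjects. Under those assumptions the choice of numerator can turn a significant primary result into a non-significant one, or the reverse. It makes no difference only if every referred subject is implanted by the time point.

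**What to change.** In section 11.1, Primary Objective #2:

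1. Change the formula to SND subjects referred for an IPG by time t, divided by subjects with an SND diagnosis, × 100.
2. Change the rate to subjects referred per person-year from SND diagnosis.
3. Change the Poisson outcome to subjects with a referral.
4. Reword the first time-point sentence to time from diagnosis to referral. It also names the proportion diagnosed as the quantity evaluated, which should become the proportion referred.
5. Reword the second time-point sentence so that its reason concerns referral.

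Implants stay with Secondary Objective #1.

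Two checks go with this:

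- **Time grid and offset.** Confirm that the 3-month grid and the offset from diagnosis suit an event that may be recorded at the diagnosis visit. Table 1 and section 5.4 collect final diagnosis and treatment decision at the same type of visit. State how a subject with no time in study after diagnosis is handled.
- **Case report forms.** Appendix B says these were still being developed. Confirm that they capture referral and its date, and add the field only if it is missing.

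The cost is wording in five places and two checks, with no extra patients and no extra test.

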1. INTRODUCTION

1.1. Study Purpose

Medtronic, is sponsoring a quality improvement study called Brady MX. It is hypothesized that lack of awareness of treatment and diagnostic pathways results in lower number of referrals to implanters of IPGs

- Education and process improvement initiatives can improve the diagnosis and increase appropriate therapy applications for SND
- The quality improvement methods to be studied will have general applicability which can be utilized beyond the Brady MX study.

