11. STATISTICAL METHODS AND DATA ANALYSIS

Medtronic statisticians or designees will conduct all statistical analysis. The sample size package PASS 2008 was used for sample size evaluation. In this study, it is hypothesized that the use of a practice-specific process improvement intervention consisting of education, diagnostic algorithm(s) and documentation tools that advocate and reinforce adherence to consensus treatment guidelines will improve the quality of care for patients with sinus node dysfunction (SND). The two primary endpoints are the impact of the intervention on the diagnosis of subjects with SND and whether SND indicated subjects receive a referral for an IPG therapy. In current practice, both of these proportions are unknown but have been estimated for a set of patients meeting the study inclusion criteria. The sample size calculations will use exact confidence intervals and tests to compare rates and binomial proportions.

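### Primary Objective #2 tests referral only among diagnosed subjects, a denominator the intervention is meant to change; a supportive all-enrolled referral comparison should be added beside it

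*Combined protocol and SAP*

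**What the plan says.** Section 4.1 lists two primary objectives: the impact of the intervention on SND diagnosis, and its impact on SND subjects receiving a referral for an indicated IPG.

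For Objective #1, Section 11.1 divides the number diagnosed by the number enrolled. For Objective #2 it limits the analysis to subjects who obtain a diagnosis: "the number of subjects with an SND diagnosis will be included in the denominator". The accompanying Poisson model starts its time at diagnosis, so it is conditional on diagnosis too.

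The sample size text covers Objective #1 only. It posits "a Phase I SND percentage of 10% at 6 months and a Phase II SND percentage of 20% at 6 months", with the conditions "If 200 subjects are collected each in Phase I and in Phase II" and "assuming a type I error of 0.05 and power of 0.80". Allowing that "the study attrition rate may be 5% of the study population", it sets at least 210 enrolled per phase.

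For Objective #2 there is no referral rate, detectable difference, sample size or power. The introduction to Section 11 says of the two primary proportions that "both of these proportions are unknown but have been estimated for a set of patients meeting the study inclusion criteria", but gives no referral figure.

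Section 1.1 states the motivating problem as a count: "lack of awareness of treatment and diagnostic pathways results in lower number of referrals to implanters of IPGs". No comparison of referrals among all enrolled subjects is planned.

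**The concern.** The Objective #2 denominator is the Objective #1 outcome. If the intervention raises diagnosis as hoped, Phase II diagnosed subjects will include people who would have stayed undiagnosed in Phase I. Those extra cases may be referred at a different rate, so the two diagnosed groups need not be comparable even if enrolled patients are alike in both phases.

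The planned ratio can then move opposite to the quantity in Section 1.1, and a reader could conclude that referral worsened when more patients per enrolled subject were being referred. The groups are also small, and the plan does not tell the reader how small or what the test can detect.

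**Working it through.** **Inputs.** From Section 11.1: 200 evaluable and 210 enrolled per phase, diagnosis 10% and 20%, alpha 0.05, two-sided hypotheses, an exact test (taken here as Fisher's). Referral rates are assumptions, because the plan gives none.

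**1. The plan's own figure (Objective #1).** Pooled normal formula:

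n = [1.960 × √(2 × 0.15 × 0.85) + 0.842 × √(0.10 × 0.90 + 0.20 × 0.80)]² / 0.10² = 199 per phase.

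The stated 200 reproduces. Fisher power at 200 per phase is 76.8%. Attrition: 200 × 1.05 = 210, as stated.

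**2. Expected denominators for Objective #2.**
- 200 per phase: 200 × 0.10 = 20 and 200 × 0.20 = 40.
- 210 per phase: 21 and 42.

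The 20% is the plan's example of a detectable effect. If diagnosis does not rise, about 20 versus 20 remain.

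**3. Power of the planned conditional test** (Fisher, 20 versus 40, 20-point rise):

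| Assumed referral among diagnosed | Power |
|---|---|
| 30% to 50% | 25% |
| 40% to 60% | 23% |
| 50% to 70% | 29% |
| 60% to 80% | 32% |
| 70% to 90% | 44% |

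Starting from 50%, 80% power needs about 86% in Phase II. The result depends on the diagnosis rate: at an assumed 30% and 40% of 210 (63 versus 84), 50% versus 70% has 66% power.

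**4. How the ratio can reverse (assumed example, 200 enrolled per phase).**
- Phase I: 20 diagnosed, 12 referred. Conditional 12/20 = 60%; per enrolled 12/200 = 6%.
- Phase II: the same 12 of 20, plus 20 newly detected cases of whom 6 are referred. Conditional (12 + 6)/40 = 45%; per enrolled 18/200 = 9%.

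No referral is lost and six are added, yet the planned proportion falls by 15 points. The all-enrolled test would reach significance for 6% versus 9% only 16% of the time. Its value here is an estimate that points the right way, not a likely significant result.

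**5. Behaviour of an all-enrolled comparison.** The rate is diagnosis rate × referral rate among diagnosed. Fisher, 210 per phase:

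| Scenario (assumed) | All-enrolled rates | All-enrolled test significant | Conditional test power |
|---|---|---|---|
| Referral fixed at 50%, diagnosis 10% to 20% | 5% vs 10% | 43% | no referral effect to detect |
| Referral fixed at 90%, diagnosis 10% to 20% | 9% vs 18% | 74% | no referral effect to detect |
| Referral 70% to 60%, diagnosis 10% to 20% | 7% vs 12% | 36% | not calculated |
| Referral 50% to 70%, diagnosis stays 10% | 5% vs 7% | 9.8% | 15.8% (21 vs 21) |
| Referral 50% to 90%, diagnosis stays 10% | 5% vs 9% | 30% | 76% (21 vs 21) |

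The all-enrolled comparison responds to a pure diagnosis effect, can look favourable when referral among diagnosed subjects worsens, and is weaker when only referral changes.

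**The case against.** The strongest defence is that the SND denominator is what the objective asks for. Sections 4.1 and 11.1 separate two steps, diagnosis among enrolled and referral among diagnosed, and referred per enrolled is their product. Making it the test would remove the only primary test of referral behaviour and partly repeat Objective #1. This stands, and it is why the conditional test should be kept.

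A reader might set 29% power for the conditional test against 87% for the all-enrolled one (5% versus 14%, 210 per phase) and infer that the latter should replace it. The documents do not support that. The two tests address different null hypotheses, and much of the 87% comes from the assumed doubling of diagnosis. The pair also mixes 200 and 210 per phase: at 210, the conditional figure is 27%.

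A reader might also infer that the planned test will probably miss a real rise. That rests on assumed referral rates, and on a 10% diagnosis rate that the plan itself calls conservative.

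Finally, it is conjecture that Phase II will find different cases. An all-enrolled denominator is not fully protected either: the phases are sequential, and Ancillary Objective #4 asks whether the intervention changes screening and enrollment. Both points are fair. They limit what the added analysis can show, but they do not make the conditional proportion sufficient alone.

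**Conclusion.** The concern holds as a gap in prespecification; the conditional test itself is not wrong. Objective #2 conditions on the outcome of Objective #1, with about 20 versus 40 subjects on the plan's example rates, and nothing planned would show a reader that referrals per enrolled subject had risen while the conditional proportion fell. The 60% to 45% reversal shows what is possible and is not a forecast.

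The low power (23% to 44% for a 20-point rise at 20 versus 40) rests on assumed referral rates and on the plan's diagnosis example. It is a reason to state the expected denominators and power, not to change the primary test. A supportive all-enrolled analysis is an inexpensive safeguard against misreading the result.

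**What to change.** In Section 11.1, Primary Objective #2:

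1. Keep the conditional proportion as the test and report the difference between phases with an exact confidence interval.
2. Add a prespecified supportive comparison of IPG referrals among all enrolled eligible subjects, counting undiagnosed subjects as not referred. It could use 6 months of follow-up, a time point both primary objectives already share. Label it the total effect of diagnosis plus referral, and state that it is interpreted only next to the conditional result.
3. State the expected denominators (20 and 40; 21 and 42 at 210 enrolled) and the power of the conditional test under named referral assumptions, for example 29% for 50% versus 70% at 20 versus 40, and 66% at 63 versus 84.
4. Reconcile the numerator in the same edit. The endpoint formula counts subjects receiving an IPG and the Poisson model counts implants, whereas the analysis-set text counts referrals.

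**Cost.** Plan wording and one further analysis. Objective #1 already requires the enrolled count and Objective #2 the referral count, so no extra patients or visits are needed.

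**Downside.** The supportive rate can be significant with no change in referral behaviour (43% and 74% in the fixed-referral scenarios), is weaker when only referral changes, and does not remove confounding from sequential phases. The text should say so.
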